### 2. Rationale and Specific Aims

### Rationale:

Hypertrophic burn scars are experienced by more than 70% of burn victims. They are a major source of decreased quality of life in burn patients due to pain, decreased range of motion, and poor cosmetic appearance. Current treatment strategies (including fat grafting and laser resurfacing) are either highly invasive, prohibitively costly, or painful. Autologous PRP does not

require anaesthesia, and is an inexpensive, safe, fast, and less painful alternative that has been recognized for its role in reducing scars associated with acne, among other things. While PRP has not been studied specifically in burn scars, there is sufficient theoretical and practical evidence that it will improve the appearance and feel of these debilitating scars, representing a large potential benefit for these patients with minimal associated risk. The evidence supporting our proposal can be seen in section 3 of the protocol.

# Specific Aims:

(1) Compare the effectiveness of intradermally-injected autologous platelet-rich plasma versus normal saline to improve burn scars, as measured by both clinician-reported (Vancouver scar scale; VSS) and patient-reported measures (Patient and Observer Scar Assessment Scale; POSAS).

(2) Compare the effectiveness of intradermally-injected autologous platelet-rich plasma versus normal saline as a control to improve neuropathic pain associated with burn scars.

(3) Understand the mechanism of action of PRP in improving burn scars via histological analysis of collagen content in the burn scar tissue biopsy specimens.

# 3. Animal Studies and Previous Human Studies

# i. Cervelli, V., Nicoli, F., Spallone, D., Verardi, S., Sorge, R., Nicoli, M., & Balzani, A. (2012). Treatment of traumatic scars using fat grafts mixed with platelet-rich plasma, and resurfacing of skin with the 1540 nm nonablative laser. Clinical and Experimental Dermatology: Experimental dermatology, 37(1), 55-61.

This study in 60 human subjects found that the combination of PRP-enriched fat grafting underneath the scar along with nonablative laser resurfacing of the scar was more effective at reducing the severity of traumatic scars than either PRP-enriched fat grafting or nonablative laser resurfacing alone, as measured by the Manchester scar scale. Fat grafting is a recognized treatment to improve the appearance and feel of scars, but this study confirmed that fat grafts that are enriched with PRP also improve the appearance of scars, especially when combined with laser resurfacing. Unfortunately, this study did not directly compare the use of fat grafting without PRP to fat grafting with PRP. One drawback to fat grafting is that it frequently requires anaesthesia and operating room time in order to harvest the fat (e.g., from the abdomen or flanks), which significantly increases the time, cost and risks associated with the procedure. By contrast, when used alone, autologous PRP is fast and low-cost, can be done in the clinic, and poses minimal risk to the patient. Of note, in this study, the only side effect noted was mild transient erythema (duration of 2-3 days) and swelling (1-2 days).

# ii. Prochazka, V., Klosova, H., Stetinsky, J., Gumulec, J., Vitkova, K., Salounova, D., ... & Ocelka, T. (2014). Addition of platelet concentrate to Dermo-Epidermal Skin Graft in

# deep burn trauma reduces scarring and need for revision surgeries. Biomedical papers of the Medical Faculty of the University Palacky, Olomouc, Czechoslovakia, 158(2), 242.

This study aimed to determine if platelet concentration in combination with autologous dermoepidermal skin grafts (DESG) led to decreased pain and shorten hospital stays as compared to DESG alone. Eighteen patients with second or third degree burns received autologous platelet concentrate and were evaluated using digital photography, standardized scales, and laser Doppler imaging. The study determined that the combination of both APC and DESG led to decreased pain, use of analgesics, antipruritics, orthotic devices, and earlier discharges.


This study represents a case of a forty-year-old woman who presented with a second-degree burn to her right abdominal flank obtained 7 weeks prior secondary to liposculpture. On admission her scar was scaled as an 11 on the Vancouver scar scale (VSS) and a 49 on the Patient scar assessment scale (PSAS). Treatments of autologous platelet-rich plasma with platelet concentrations between 300% and 400% were applied to the edges of the burn on days 0, 30, 60, 90, 120, and 180. Ten months out from initial presentation, the patient's VSS had dropped to 2 and her PSAS had dropped to 10. Most notably, her pain had dropped from an 8 on initial presentation to a 0. This case report, in combination with the study done in rats by Huang et al, leads us to believe that PRP may be a potential treatment for reducing neuropathic pain in burn scar patients. Our study will be the first to investigate pain outcomes in relation to treatment of burn scars with PRP.

# iv. Asif, M., Kanodia, S., & Singh, K. (2016). Combined autologous platelet-rich plasma with microneedling verses microneedling with distilled water in the treatment of atrophic acne scars: a concurrent split- face study. Journal of cosmetic dermatology, 15(4), 434-443.

This study aimed to investigate the efficacy of combining platelet rich plasma with microneedling in the treatment of atrophic acne scars. Fifty patients received microneedling on both halves of their faces. Each patient also received intradermal injections and topical applications of PRP on the right side of their face and intradermal injections of distilled water on the left side of their face. The patients received these treatments each month for three months, and were evaluated using the Goodman's Quantitative and Qualitative scales. Using the Quantitative scale, the right halves of patient's faces showed a 62.20% improvement compared to only 45.85% improvement on the left. Additionally, 40% of patients indicated that the right side of their face had an excellent response on the Qualitative scale compared to only 10% on the left side. This

study concluded that PRP in combination with microneedling was more effective at treating atrophic acne scars than microneedling alone.

# v. Klosová, H., Štětinský, J., Bryjová, I., Hledík, S., & Klein, L. (2013). Objective evaluation of the effect of autologous platelet concentrate on post-operative scarring in deep burns. Burns, 39(6), 1263-1276.

This study sought to use an objective measurement to determine the effect of platelet rich plasma on post-operative scarring in patients with deep burns. Rather than using a subjective scale such as the Vancouver Scar Scale or the Patient and Observer Scar Assessment Scale, this study utilized the Cutometer MPA 580 to measure the viscoelastic parameters of the skin. Twenty-three patients with 38 scars were enrolled, and received treatment with either split thickness skin grafting (STSF) alone or STSF in combination with autologous platelet concentrate (APC). Treatment with APC in combination with STSF resulted in a more rapid return of viscoelastic properties to baseline (normal skin) as compared to treatment with STSF alone.

# vi. Alser, O. H., & Goutos, I. (2018). The evidence behind the use of platelet-rich plasma (PRP) in scar management: a literature review. Scars, Burns & Healing, 4, 2059513118808773.

This review article summarizes findings from several studies on clinical applications of PRP for burn scars, surgical scars, and as adjunct treatment of scars with CO2 laser and fat grafting:

# a. Lee, J. W., Kim, B. J., Kim, M. N., & Mun, S. K. (2011). The efficacy of autologous platelet rich plasma combined with ablative carbon dioxide fractional resurfacing for acne scars: a simultaneous split-face trial. Dermatologic Surgery, 37(7), 931-938.

Lee et al. used PRP as an adjunct to ablative fractional laser treatment in a split-face study of 14 Korean patients with analysis by blinded dermatologists. The experimental group received injections of PRP after treatment with ablative fractional laser and the control group received saline injections after treatment. It was found that the PRP adjunct group experienced shorter duration of post-treatment erythema and edema  $(6.1\pm1.1 \text{ vs}. 7.1\pm1.5 \text{ days and } 5.9\pm1.1 \text{ vs}. 6.8\pm1.0 \text{ days, respectively})$  and showed greater overall improvement on a quartile grading scale  $(2.7\pm0.7 \text{ vs}. 2.3\pm0.5)$ . Crusting was experienced by both treatment groups and no other adverse effects measured (petechiae, oozing, dyschromia, infection, scarring, or blistering) were experienced by any participant in either group.

# b. Abdel Aal, A. M., Ibrahim, I. M., Sami, N. A., & Abdel Kareem, I. M. (2018). Evaluation of autologous platelet-rich plasma plus ablative carbon dioxide

# fractional laser in the treatment of acne scars. Journal of Cosmetic and Laser Therapy, 20(2), 106-113.

Abdel et al. conducted a similar study to use PRP as an adjunct to ablative fractional laser treatment for atrophic acne scars but did not inject saline on the control side. This study also found better overall improvement and faster resolution of edema, it notably reported no post-inflammatory pigmentation on the PRP treated side and significantly lower incidence of post-treatment acneiform eruption. Patient satisfaction was higher on the PRP treated side as well.

# c. Tehranian, A., Esfehani-Mehr, B., Pirjani, R., Rezaei, N., Heidary, S. S., & Sepidarkish, M. (2016). Application of autologous platelet-rich plasma (PRP) on wound healing after caesarean section in high-risk patients. Iranian Red Crescent Medical Journal, 18(7).

Tehranian et al. conducted a study examining use of PRP on scar healing from elective cesarian section. PRP was applied to subcutaneous tissue before closure in one group and the other group received saline irrigation before closure. Measurements included REEDA and VSS for scar healing and the PRP-treated group experienced greater reduction in these scores than the control group (85.5% reduction vs. 72% reduction in REEDA and 54% reduction vs. 18% reduction in VSS).

# **d.** Gentile, P., De Angelis, B., Pasin, M., Cervelli, G., Curcio, C. B., Floris, M., ... & Insalaco, C. (2014). Adipose-derived stromal vascular fraction cells and plateletrich plasma: basic and clinical evaluation for cell-based therapies in patients with scars on the face. Journal of Craniofacial Surgery, 25(1), 267-272.

Gentile et al. conducted a study on burn and traumatic scars comparing the efficacy of fat graft treatment enhanced by stromal vascular fraction or PRP. A control group of centrifuged fat without adjunct therapy was also used. In fat grafting supplemented with PRP, there was 69% maintenance of contour vs only 39% of the control group. Less resorption of injected fat was also observed compared to control.

# vii. Huang, S. H., Wu, S. H., Lee, S. S., Lin, Y. N., Chai, C. Y., Lai, C. S., & Wang, H. M. D. (2018). Platelet-Rich Plasma Injection in Burn Scar Areas Alleviates Neuropathic Scar Pain. International journal of medical sciences, 15(3), 238.

This study in rats found that burn-induced neuropathic pain associated with burn scars was reduced after PRP was injected subcutaneously into mature burn scars, as measured by behavior tests and immunohistochemistry staining of burned skin and spinal cord dorsal horns. Specifically, PRP alleviated allodynia in burn-induced neuropathic pain four weeks after PRP treatment, and modulated several neuroinflammatory markers and pathways including PTEN, mTOR, and TNF- $\alpha$  in such a manner as to attenuate neuropathic pain. The role of PRP in

reducing burn scar neuropathic pain in humans has yet to be studied, and because of this work in rats, it is one of the aims of this present study.

viii. Venter, N. G., Marques, R. G., dos Santos, J. S., & Monte-Alto-Costa, A. (2016). Use of platelet-rich plasma in deep second-and third-degree burns. Burns, 42(4), 807-814. This study in rats found that deep second-degree burn wounds that were treated with topical autologous PRP at the time of the burn (immediately after) displayed a greater percentage of wound closure at 21 days when compared to control (burn without PRP). They also found that on histological analysis, the PRP treatment was associated with larger neo-epidermis thickness in deep second-degree burns. In sum, these findings indicate that PRP can hasten wound healing when applied to an acute burn wound. Two important differences exist between our model and this rat model: (1) we will be using the PRP on mature burn scars which have already re-epithelialized, and because of this re-epithelialization, (2) we will be injecting the PRP subcutaneously to allow the PRP to interact directly with the collagen and cells beneath the epidermis.

# 4. Inclusion/Exclusion Criteria

Inclusion Criteria:

- 18-70 years old, all sexes
- Thermal burn scar on the trunk or abdomen ≥ 1 year old that meets ONE of the following criteria:
  - Vancouver Scar Scale score  $\geq 7$
  - Patient and Observer Scar Assessment Scale (POSAS) score ≥ 35
  - Neuropathic symptoms
    - POSAS score ≥ 5 on question evaluating itchiness
    - POSAS score  $\geq$  5 on question evaluating pain

Exclusion Criteria:

- Initial burn injury was less than 1 year old
- History of chemical or electrical burn
- History of CO2 treatment to the scar of interest
- Genetic or acquired conditions that severely affect systemic wound healing or collagen formation (vasculitis, diabetes, Ehlers-Danlos syndrome, radiation therapy to the scar site or use of immunosuppressive medications within the last year, active cancer)

# 5. Enrollment/Randomization

Prior to enrollment, all sixty potential study ID numbers will be randomly assigned to a treatment group (Right/Left). The randomization will be performed by coin flip (heads is right, tails is left). This will be logged in a secure REDCAP form only accessible by the researcher not conducting scar evaluations (unblinded REDCAP). There will be a secondary REDCAP form used for logging VSS/POSAS scores that does not contain this information (blinded REDCAP).

Potential candidates will be identified by the attending surgeon at the Burn Reconstruction Clinic at Vanderbilt. All patients meeting preliminary inclusion/exclusion criteria will be contacted, via phone or in person at the clinic, and given a brief description of the study. If interested in participating, inclusion/exclusion criteria will be reviewed with the patient, and the patient will be scheduled for their first appointment. Patients will be assigned to a study ID number (with associated treatment group) based on order of enrollment.

## 6. Study Procedures

# Day 1:

When the patient first arrives, they will be given a copy of the patient POSAS, the study information sheet, and the demographics sheet to review and fill out while in the waiting room. The demographics sheet will collect the following demographic information: MRN, date of birth, sex, %TBSA, comorbidities (diabetes, smoking, hypertension, history of radiation or chemotherapy, history of cancer), presence of skin graft and type (xeno- or allograft) and location, size and donor site of skin graft used, race, Fitzpatrick skin type, mechanism of injury (e.g., flame, scald, radiator, etc.), current medications (in particular, any anti-inflammatories, anti-neoplastics, or steroids), and prior scar treatments, including over the counter creams or lotions.

Once roomed, a provider will administer both the VSS and the observer POSAS to confirm that the patient meets inclusion criteria. A secondary provider will also administer a VSS and POSAS.

After determining that the patient meets inclusion criteria, the consent form will be reviewed in depth to describe the purpose and procedures associated with the study. The consent form, demographics form, and VSS/POSAS scores will be logged into the blinded REDCAP.

For the procedure itself, 6mL of anticoagulant citrate dextrose A (ACD-A) will be drawn up in a 60mL syringe, after which 44 mL of the patient's own venous blood will be drawn into the same 60mL syringe using standard venipuncture techniques (Bellus Medical, 2019). While patient is waiting in the examination room, the sterile tubes of blood will be centrifuged by the ELMI CM-7S centrifuge which takes approximately 10-15 minutes. While waiting for the PRP to undergo centrifugation the scar to be treated will first be wiped with an alcohol swab, then measured and marked out with a marking pen such that the entirety of the scar will fit into a rectangle that is drawn, and the rectangle is filled entirely with the scar tissue. A ruler will be used to measure the scar in its greatest horizontal span, and the midway point will be marked with a vertical line. The length and height of the rectangle will be recorded. The vertical and horizontal distance from the nearest point-like anatomic landmark (e.g., xiphoid process) to the two edges of the rectangle will be documented so that the rectangle can be recreated at a later date. A photo of the outlined scar(s) will be obtained with a digital camera, with a ruler in view placed against the skin adjacent to the scar for reference as well as a "L" and "R" to designate laterality. The area inside the rectangle will then be subdivided with a marking pen into 1cm x 1cm square boxes, with the plan of injecting 1mL of either PRP or normal saline into each 1 square cm box.

The unblinded researcher who does not participate in the scar assessments will review the unblinded REDCAP containing the pre-designated treatment group (termed "Right and Left") and will inject the PRP and saline into the scar. The syringes will be covered with a white sticker and labeled such that the patient is unable to infer which syringe contains PRP (PRP is yellow

with a red hue and normal saline is clear). The unblinded researcher will then log this treatment into the unblinded REDCAP.

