# One Month Status-Post First Treatment (Day ~30):

At the one-month follow-up visit, the patient's treated scar will be identified with the assistance of old photos and measurements, and the rectangle will be re-marked out. The patient's blood will be collected in the same manner as Day 1 and spun down in the ELMI centrifuge. The patient and blinded providers will complete the VSS and POSAS while waiting, and the scar will then be marked into 1cm squares for subsequent treatment. The two different halves of the scar will be treated with the same substance that they were in the first round by the unblinded researcher.

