# Two Months Status-Post First Treatment (Day ~60):

The two-month follow-up visit will follow the same protocol as the one-month visit.

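### No half-scar baseline is described: Day 1 VSS/POSAS come before the midline that defines the randomised halves, and no visit says scores are recorded by half

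*Combined protocol and SAP*

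**What the plan says.** **Unit of randomisation and treatment.** Under Section 5, study numbers are "randomly assigned to a treatment group (Right/Left") by coin flip. In Section 6, the one-month visit repeats the allocation by half: "The two different halves of the scar will be treated with the same substance that they were in the first round". The month 5 and one-year biopsies are also taken by side.

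**Day 1 order (Section 6, Day 1).**
1. On arrival in the waiting room, patients complete their own scale: "they will be given a copy of the patient POSAS".
2. "Once roomed, a provider will administer both the VSS and the observer POSAS to confirm that the patient meets inclusion criteria". A second provider then scores too.
3. Consent is reviewed and the scores are filed: "The consent form, demographics form, and VSS/POSAS scores will be logged into the blinded REDCAP".
4. Blood is drawn. During the spin the scar is outlined and "the midway point will be marked with a vertical line". A photograph with L and R labels is taken.
5. The unblinded researcher injects.

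No VSS or POSAS is described between steps 4 and 5. The eligibility thresholds in Section 4 apply to the scar, not to a half.

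**Follow-up.** At month 1: "The patient and blinded providers will complete the VSS and POSAS while waiting, and the scar will then be marked into 1cm squares". For month 2, "The two-month follow-up visit will follow the same protocol as the one-month visit", and months 3 and 4 are described in the same way. At month 5 and one year, scoring precedes the biopsy. None of these visits says whether there is one score per scar or one per half.

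**Analysis.** Section 10 plans comparisons between groups before and after treatment, and a Wilcoxon signed rank test within groups before and after treatment.

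**The concern.** In a split-scar design the groups are sets of halves, so a before value for a group has to belong to a half. Following Day 1 as written, the patient rates the scar before any dividing line exists, and the providers rate it to answer a question about the whole scar. That sequence does not deliver a Left and a Right baseline. The gap cannot be closed later, because month 1 already follows the first injection.

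Two things are at stake. First, the within-group before/after test may compare a half with a whole, so part of any apparent improvement could come from the change of scoring unit. Second, the paired PRP-versus-saline comparison loses the option of adjusting for how the two halves differed at the start.

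**Working it through.** **Inputs from the documents.** n = 35 planned patients and a 0.05 significance level (Section 10). As a check on n, 35/(1 − 0.10) = 38.9, so 39 patients, consistent with the 40 to be recruited. The plan gives no SD, correlation or half-to-half gap, so these are assumed below and shown as ranges. A two-sided test is also assumed. Higher scores mean a worse scar.

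**1. PRP-versus-saline contrast at follow-up.** Let W be one whole-scar Day 1 score and F the half-level follow-up score.

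(F_PRP − W) − (F_saline − W) = F_PRP − F_saline

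W cancels. The side is randomised, so this contrast is unbiased. It simply has no baseline adjustment.

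**2. Within-group before/after change, F − W.** Let M be the mean of the two halves at baseline, G the absolute Left–Right gap, and W = M + k·G/2. Here k = 0 means the whole-scar score is the mean of the halves, k = 1 means it follows the worse half, and k = 0.5 is midway. Because the side is randomised, a treated half averages M. With no true effect the expected change is

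E(F − W) = −k × E(G)/2

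For mean gaps of 0.5, 1 and 2 points this is 0 at k = 0; −0.125, −0.25 and −0.5 at k = 0.5; and −0.25, −0.5 and −1.0 at k = 1. It appears equally in the PRP and saline groups.

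Rejection rate of the signed rank test, simulated with n = 35, no true effect, half-normal gap and normal follow-up noise:

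| Whole-scar score | Noise SD | Gap 0.5 | Gap 1 | Gap 2 |
|---|---|---|---|---|
| Mean of halves | 2 | 4.8% | 4.6% | 4.7% |
| Midway | 2 | 6.5% | 10.4% | 18.8% |
| Worse half | 2 | 11% | 26% | 59% |
| Worse half | 3 | 7% | 14% | 37% |
| Worse half | 4 | 6% | 11% | 25% |

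At SD 3 to 4 the midway rates fall, to about 5% at the smallest gap. The shape of the gap distribution also matters: a fixed 2-point gap at SD 2 under the worse-half rule gives 70% rather than 59%.

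**3. Precision forgone.** Let r be the correlation between the baseline and follow-up half-differences. Regressing the follow-up difference on the baseline difference changes the variance, relative to follow-up only, by

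(1 − r²)(1 + 1/(n − 3)) = (1 − r²)(33/32)

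| r | Factor | 35 pairs act like |
|---|---|---|
| 0 | 1.031 | 33.9 |
| 0.3 | 0.938 | 37.3 |
| 0.5 | 0.773 | 45.3 |
| 0.7 | 0.526 | 66.5 |

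Break-even is r = √(1/33) = 0.17. Simple change scores have the factor 2(1 − r), which is 1.40, 1.00 and 0.60 at r = 0.3, 0.5 and 0.7, so they gain only above r = 0.5. A gain is therefore possible but not assured.

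**The case against.** The strongest reply is that half-level scoring was plainly intended. The aims compare PRP with saline, allocation and injection are by side, and the analysis speaks of groups. The score form is not in the documents and may have Left and Right fields, on Day 1 as well. A rater can also judge the two sides of a scar before a line is inked. This stands as a limit on certainty: the documents show that no half-level baseline is described, not that none will be collected. It does not repair the described order, in which the patient scale is completed before the halves are marked out and the providers score for eligibility of the scar.

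It is also fair that the half-versus-whole mismatch needs two conditions together, whole-scar scores on Day 1 and half-level scores later. Further, a within-group before/after test is weak evidence of a PRP effect in any case: patients can qualify through a high score, so regression to the mean could show improvement in both halves even with a sound half-level baseline.

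The Day 1 photograph with side labels offers partial recovery. It could support later rating of visible features by side, but not itch, pain or pliability.

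A reader might infer that the trial cannot estimate PRP versus saline at all. That would follow only if every visit yielded a single score per scar, and the documents do not show that this is planned. A reader might also infer that the main contrast is biased; the cancellation of W shows that it is not.

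**Conclusion.** The point holds as a gap in the described procedure that should be fixed. Confidence is high that Day 1 scoring precedes the midline with no described repeat before injection, and medium on the scoring unit at any visit.

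If Day 1 is whole-scar and follow-up is by half, the within-group test in Section 10 does not compare like with like. Its false-positive rate at n = 35 would be about 5% if the whole-scar score equals the mean of the halves, about 5% to 19% if midway, and about 6% to 59% if it follows the worse half. These figures are illustrative: they rest on assumed noise SDs of 2 to 4 points and mean gaps of 0.5 to 2 points. For the PRP-versus-saline comparison the cost is lost opportunity rather than bias: with adjustment, 35 pairs would act like about 34 to 67 for assumed r from 0 to 0.7.

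**What to change.** - **Section 6, Day 1.** After consent and marking of the midline, and before any injection, have the patient score the patient POSAS and the same two blinded providers score VSS and observer POSAS, separately for Left and Right and including itch and pain. Name this the baseline. Keep the earlier score for eligibility only.
- **Section 6, every follow-up visit, including month 5 and one year.** Re-mark the midline before scoring and record Left and Right separately in the blinded REDCap. At month 1 the rectangle is already redrawn before scoring; redrawing of the midline is not stated.
- **Section 10.** Define the observation as the half-scar score, so that before and after values refer to the same half and PRP and saline halves are compared as pairs within the patient. Which test is the main one is a separate analysis-plan question and need not be settled for this change.

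**Cost.** One Left/Right assessment per rater is added on Day 1, with a sentence per visit on the scoring unit and side-labelled fields if the form lacks them. If follow-up was meant to be whole-scar, one more score per rater is needed at each of the six follow-up visits. This is a few extra minutes per visit for the existing assessors, partly outside the 10 to 15 minute spin, with no added staff or procedures.

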#### **10. Statistical Considerations**

-Our proposed study is methodically similar to "Treatment of traumatic scars using fat grafts mixed with platelet-rich plasma and resurfacing of skin with the 1540 nm non-ablative laser" by Cervelli et al., and we expect to analyze a similar population and outcome. In this study, they

met power with 31 patients. We will plan to enroll 35 patients, but we will recruit 40 with an expected 10% attrition.

-In our study, data will be recorded in a spreadsheet (Excel; Microsoft Corp., Redmond, WA, USA) and analyzed with SPSS software for Windows (version 15.0; SPSS, Chicago, IL, USA). Descriptive statistics will include mean ± SD for parametric variables, and median and range for nonparametric variables. The median will be used to test the difference between the groups before and after treatment, and the Wilcoxon signed rank test will be used to examine differences within groups before and after treatment. P<0.05 will be considered significant.

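### Day 1 scores both confirm entry on lower cut-offs and are the only pre-treatment scores for the before-after test, so some fall can occur without any treatment effect.

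*Combined protocol and SAP*

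**What the plan says.** - **Entry rule (Section 4).** The scar qualifies if it "meets ONE of the following criteria": VSS of at least 7, POSAS of at least 35, or a POSAS itch or pain item of at least 5. All are lower cut-offs.
- **Day 1 scoring (Section 6, Day 1).** The patient fills in the patient POSAS on arrival. Then "a provider will administer both the VSS and the observer POSAS to confirm that the patient meets inclusion criteria". The next sentence reads "A secondary provider will also administer a VSS and POSAS". The role of this second reading is not stated, and it comes before the sentence about eligibility having been determined. The scores are kept as study data: "The consent form, demographics form, and VSS/POSAS scores will be logged into the blinded REDCAP".
- **Next scoring (Section 6, one-month visit).** The first injection is given on Day 1. Scoring resumes at about Day 30: "The patient and blinded providers will complete the VSS and POSAS while waiting". No other pre-treatment scoring is described.
- **Analysis (Section 10).** The only named test is this: "the Wilcoxon signed rank test will be used to examine differences within groups before and after treatment", with significance at P<0.05. A between-group difference is mentioned, but it is tied to the median and no test is named. The 'before' value is not defined.
- **Design (Sections 2 and 5).** The aims compare PRP with saline. The treated side is assigned by coin flip within each patient.

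**The concern.** A reading is the scar's true score plus error. A scar near the cut-off is admitted when the error is upward and turned away when it is downward. Admitted readings therefore sit too high on average, and a fresh reading of the same unchanged scar is lower. This is regression to the mean.

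If the admitting reading is also the 'before' value, the before-after test picks up that fall. A significant fall in the PRP half could then be reported as improvement when nothing has changed. The saline half would show the same fall, but the plan names no test that sets one half against the other. The one inferential result it does specify is the one exposed to this bias.

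**Working it through.** **Inputs from the documents.** Cut-offs and entry rule from Section 4; 35 patients and P<0.05 from Section 10. As a check on the sample size, 35/(1-0.10) = 38.9, or 39, and the plan rounds up to recruiting 40. Section 10 gives no SD, effect size or power.

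**Assumptions, not in the documents.** Reliability of a single reading (rho) 0.6 to 0.9; independent rating errors; no true change; two-sided tests. VSS-scale runs use a reading SD of 2 and a candidate mean of 6 to 8. Runs in SD units use normal scores and, for the four-criterion rule, a correlation of 0.5 between true scores and equally placed cut-offs.

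**Step 1: everyone enters on the analysed score.** With the cut-off c SDs above the clinic mean, the expected fall in SD units is (1 - rho) × phi(c) / (1 - Phi(c)). The last column is the simulated rate of P<0.05 for the Wilcoxon test in the PRP half.

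| rho | c | Expected fall (SD) | Falsely positive |
|---|---|---|---|
| 0.9 | -0.5 | 0.10 × 0.3521/0.6915 = 0.05 | 9% |
| 0.75 | 0 | 0.25 × 0.3989/0.5000 = 0.20 | 39% |
| 0.6 | 0.5 | 0.40 × 0.3521/0.3085 = 0.46 | 87% |

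On the VSS scale with whole-number scores, the fall is about 0.1 to 0.8 points and the test is positive in about 8-77% of trials. The top is lower than 87% because a score rounded to 7 needs only 6.5 before rounding. At a candidate mean of 6, c is then (6.5 - 6)/2 = 0.25, not 0.5.

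**Step 2: the plan's any-one rule.** Patients admitted on another criterion have no selected VSS error, so the average fall shrinks.

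| rho | c | Fall, all patients (SD) | Fall, those qualifying on the analysed score (SD) | Falsely positive |
|---|---|---|---|---|
| 0.9 | 0 | 0.01 | 0.08 | 5% |
| 0.75 | 0.5 | 0.04 | 0.28 | 7% |
| 0.75 | 1 | 0.07 | 0.38 | 9% |
| 0.6 | 1.5 | 0.17 | 0.77 | 16% |

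Over all the any-one scenarios run, in SD units and on the VSS scale, the rate is about 3-20%. It is near 5% when the other criteria admit many patients. It moves back towards the Step 1 range as those criteria become harder to meet. Simply imposing a mix in which half the patients enter regardless of VSS gave 6-26%.

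**Step 3: which Day 1 reading is 'before'.** Averaging an admitting reading with an independent second reading halves the excess. In the worst VSS-only case the fall went from 0.82 to 0.40 points. Using the second reading alone gave a fall of 0.00 SD and a positive rate of about 4-5%, provided its error is independent of the first and it plays no part in entry.

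**Step 4: PRP half against saline half.** The false-positive rate was about 4-7% in every scenario, which is nominal within simulation error.

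**The case against.** The strongest reply is that the trial's question is protected by design. The aims compare PRP with saline, side is randomised within the scar, and regression to the mean moves both halves equally. That stands: a reader might infer that the trial's main comparison is biased, and Step 4 shows it is not. It does not dispose of the point, because Section 10 names no test for that comparison and does name the before-after one.

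Second, the large figures describe a trial in which every patient enters on VSS. This also stands. Section 4 admits on any one of several criteria, and the documents give no reason to think VSS alone decides entry. The 8-77% range is therefore an upper scenario and should not be read as this trial's error rate.

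Third, a reader might infer that the plan takes the admitting reading as the baseline and sets the second provider's aside. The documents do not say that. They leave open the first reading, the second or an average, and more than one provider also scores at follow-up. What can be said is that the 'before' value is undefined.

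Two further points limit the remedy. The second reading is described before eligibility is declared, so it may count towards entry and be selected too. And Section 4 does not say which POSAS the cut-off of 35 refers to, so the observer score may not be the selecting one. If scores were also used in the preliminary check described in Section 5, Day 1 is already partly a re-reading.

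**Conclusion.** The concern holds in a limited form. Day 1 scores confirm entry on lower cut-offs and are the only pre-treatment scores described for the only named test. If the admitting reading serves as 'before', alone or averaged, part of any within-group fall is expected without a treatment effect.

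The size cannot be fixed from the documents, which give no SD, reliability or entry mix. With 35 patients, no true change and the stated assumptions, the before-after test would be falsely positive in about 8-77% of trials if all entered on VSS, and in about 3-20%, often near 5%, under the any-one rule. The bias may thus be negligible or several times the nominal 5%, and the plan gives no means of telling which. It threatens a claim of benefit based on change within the PRP half. It does not threaten the randomised comparison.

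**What to change.** **Section 10.** State that within-group before-after results for VSS, observer POSAS and patient POSAS are descriptive and cannot support a claim of benefit. Any such claim must rest on the paired difference between the PRP half and the saline half within patient. The patient POSAS belongs here because no second Day 1 patient reading is described, and POSAS itch and pain items are themselves entry criteria.

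**Section 6, Day 1.** State that the first provider's scores decide eligibility only. State that the second provider scores without sight of the first, that this reading is not used for entry, and that it is the 'before' value in any before-after summary of VSS and observer POSAS.

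**Cost.** For the baseline the change is wording only, since the second reading is already taken. The baseline then rests on one rater and is slightly noisier. A same-day second reading removes rater error but not day-to-day variation in the scar. The paired comparison needs each half scored separately. Section 6 does not say that this is done, so it should be stated; if it is not current practice, it adds some scoring time per visit.
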